5.4.2 Protocol Deviation

A protocol deviation (PD) is defined as any change, divergence, or departure from the IRB-approved study procedures in a research protocol and are further characterized as major and minor as follows:

- Major Deviations – Deviations from the IRB approved protocol that have, or may have the potential to, negatively impact, the rights, welfare or safety of the subject, or to substantially negatively impact the scientific integrity or validity of the study.
- Minor Deviations – Deviations that do not have the potential to negatively impact the rights, safety, or welfare of subjects or others, or the scientific integrity or validity of the study.

For the reporting purposes, failure of subjects to comply with the research protocol does not represent non-compliance unless that failure is due to an action or omission of a member of the research team, for example, the failure to give adequate instruction to the subject.

A major deviation must be reported within 7 calendar days of an investigator becoming aware of an actual or suspected deviation. Although PDs are also non-compliance, these should only be reported once as deviations. Major deviations resulting in death must be reported within 24 hours of the occurrence of the event or of any member of the study team becoming aware of the death.

Researchers are responsible for monitoring their studies throughout the year for adherence to the IRB approved protocol. The purpose of this monitoring is to identify major deviations and to look for trends in minor deviations that may indicate a systemic issue in how the study is being conducted that could potentially negatively impact the rights, safety, or welfare of participants or the study's ability to produce scientifically valid results. A series of minor deviations pointing toward a more global issue that could affect the rights, safety or welfare of the participant or affect the validity of the study should be reported as a major deviation. In all other instances, a summary of minor deviations should be provided to the IRB at the time of continuing review.

5.4.3 Non-Compliance

Non-compliance is the failure of investigator(s) to follow the applicable laws, regulations, or institutional policies governing the protection of human subjects in research, or the requirements or determinations of the IRB, whether intentional or not.

Non-compliance may be unintentional (e.g. due to lack of understanding, knowledge, or commitment), or intentional (e.g. due to deliberate choice to ignore or compromise the requirements of any applicable regulation, organizational policy, or determination of the IRB).

Non-compliance is further characterized as serious or continuing as follows:

- Serious non-compliance – Non-compliance, whether intentional or not, that results in harm or otherwise materially compromises the rights, welfare and/or safety of the subject. Non-compliance that materially effects the scientific integrity or validity of the research may be considered serious non-compliance, even if it does not result in direct harm to research subjects.
- Continuing non-compliance – A pattern of recurring non-compliance that either has resulted, or, if continued, may result in harm to subjects or otherwise materially compromise the rights, welfare and/or safety of subjects, affect the scientific integrity of the study or validity of the results. The pattern may comprise repetition of the same non-compliant action(s), or different noncompliant events.

Any actual or suspected non-compliance by any investigator or entity associated with the protocol must be reported to the IRB by the PI/designee within 7 calendar days of any investigator or individual associated with the protocol first becoming aware.

5.4.4 Death

Any death of a research subject that is possibly, probably or definitely related to the research must be reported within 24 hours of an investigator becoming aware of the death.

5.4.5 New Information

New information that might affect the willingness of a subject to enroll or remain in the study should be reported within 7 calendar days of an investigator first becoming aware.

5.4.6 Suspension or Termination of Research Activities

Any suspension or termination of research activities, including holds on new enrollment, placed upon the research by the study sponsor, NIH or IC leadership, or any regulatory agency must be reported within 7 calendar days of an investigator becoming aware.

5.4.7 Expedited Reporting to the IRB

Death related to research must be reported within 24 hours.

The following will be reported within 7 calendar days of investigator awareness:

- Actual or suspected UPs;
- Actual or suspected non-compliance;
- Actual or suspected Major PDs;
- SAEs that are actual or suspected UPs;
- New information that might affect the willingness of a subject to enroll or remain in the study;
- Suspension or termination of research activities, including holds on new enrollment, placed upon the research by the study sponsor, NIH or IC leadership, or any regulatory agency.

5.4.8 Annual Reporting to the IRB

The following will be reported to the NIAID IRB in summary at the time of Continuing Review:

- Summary of UPs and non-compliance;
- AEs, including SAEs, that are not UPs, as a narrative summary statement indicating whether these events were within the expected range;
- Minor PDs (aggregate summary);
- Any trends or events which in the opinion of the investigator should be reported.

6. STATISTICAL CONSIDERATIONS

6.1 OVERVIEW

This is a Phase I, open-label, dose escalation study to evaluate the dose, safety, tolerability, and immunogenicity of VRC-FLUNPF099-00-VP in two dose regimens. Study objectives can be found in Section 3.

6.2 ENDPOINTS

6.2.1 Primary Endpoints: Safety

Assessment of product safety will include clinical observation and monitoring of hematological and chemical parameters. Reactogenicity will be closely monitored for 7 days after each injection and safety evaluated by clinical visits for 52 weeks following the last vaccine administration and through an influenza season. See Section 4.2 and Appendix I for details and specified time points. The following parameters will be assessed for all study groups:

- Occurrence of solicited local reactogenicity symptoms for 7 days after each injection
- Occurrence of solicited systemic reactogenicity symptoms for 7 days after each injection
- Change from baseline in safety laboratory measures

- Occurrence of AEs of all severities through the 4 week post-injection visit
- Occurrence at any time throughout the study of SAEs or new chronic medical conditions that require ongoing medical management.

6.2.2 Secondary Endpoints: Immunogenicity

The principal immunogenicity endpoints will be assessed by measuring HA-stem specific antibody by pseudo-neutralization assay at:

- Group 1: Baseline (Week 0/Visit 02) and Week 2 (Visit 04) after vaccination, and
- Groups 2A-2D: Baseline (Week 0/Visit 02) and Week 2 (Visit 04) after the first vaccination, and at Week 16 (Visit 07) and Week 18 (Visit 09) after the second vaccination

6.2.3 Exploratory Endpoints: Immunogenicity

Exploratory immunogenicity evaluations may include the detection of antibody by MSD or microneutralization assay, and exploratory B and T cell assays.

6.3 SAMPLE SIZE AND ACCRUAL

Recruitment will target 53 healthy adult participants 18 to 70 years of age, though up to 70 participants may be enrolled if deemed necessary for safety or immunogenicity evaluations.

Enrollment will be spread over multiple groups. Group 1 will target 5 healthy adults 18 to 40 years of age. Groups 2A, 2B, 2C, and 2D will target 12 healthy adult participants each, with each study group corresponding to a different age range.

6.3.1 Power Calculations for Safety

The goal of the safety evaluation for this study is to identify safety concerns associated with injections of the investigational vaccine. Primary sample size calculations for safety are expressed in terms of the ability to detect serious adverse experiences. Other sample size calculations for comparing the two vaccination groups on adverse experiences are similar to the calculations for immunogenicity (Section 6.4.3).

The ability of the study to identify SAEs will be expressed in terms of the probability of observing a certain number of SAEs. Useful values are the minimum true rate such that the probability of observing at least one event is at least 90%, and the maximum true rate such that the probability of not observing any event is at least 90%.

For Group 1 (*dose-escalation*) within each group (n=5), there is a 90% chance to observe at least 1 SAE if the true rate is at least 0.369 and over 90% chance to observe no SAE if the true rate is less than 0.021.

For Groups 2A, 2B, 2C, 2D within each group (n=12), there is greater than a 90% chance to observe at least 1 SAE if the true rate is at least 0.175 and over a 90% chance to observe no SAE if the true rate is no more than 0.009.

If Groups 2A, 2B, 2C, 2D are combined (N=48), there is greater than a 90% chance to observe at least 1 SAE if the true rate is at least 0.047 and greater than a 90% chance to observe no SAE if the true rate is no more than 0.002

Probabilities of observing 0 or more than 1 SAE within each group are presented in **Table 6-1** for a range of possible true event rates and different sample sizes. These calculations provide a

complete picture of the sensitivity of this study design to identify potential safety problems with the vaccine.

Table 6-2 gives the upper and lower bounds for 95% exact binomial confidence intervals of the true SAE rate at all possible numbers of events within each group (n=5 and n=12).

For Group 1 (n=5): If none of the 5 participants receiving the vaccines experience SAEs, the 95% exact 2-sided upper confidence bound for the SAE rate is 0.52.

For Groups 2A, 2B, 2C, 2D (n=12): If none of the 12 participants receiving the vaccines experience SAEs, the 95% exact 2-sided upper confidence bound for the SAE rate is 0.265.

Table 6-1: Probability of Events for Different Safety and Immunogenicity Scenarios

True Event Rate	Group 1 (dose-escalation): N=5		Groups 2A, 2B, 2C, 2D: N=12		Groups 2A, 2B, 2C, 2D combined: N=48	
	Pr (observing 0 event)	Pr (observing more than 1 event)	Pr (observing 0 event)	Pr (observing more than 1 event)	Pr (observing 0 event)	Pr (observing more than 1 event)
0.01	0.951	0.001	0.886	0.006	0.617	0.083
0.02	0.904	0.004	0.785	0.023	0.379	0.249
0.05	0.774	0.023	0.540	0.118	0.085	0.699
0.1	0.590	0.081	0.282	0.341	0.006	0.960
0.15	0.444	0.165	0.142	0.557	<0.001	0.996
0.2	0.328	0.263	0.069	0.725	<0.001	>0.999
0.3	0.168	0.472	0.014	0.915	<0.001	>0.999
0.4	0.078	0.663	0.002	0.980	<0.001	>0.999
0.5	0.031	0.812	<0.001	0.997	<0.001	>0.999

Table 6-2: 95% Confidence Intervals for the True Rate at All Possible Observed Rates within a Group (n=5 and n=12)

Observed Rate	Group 1: N=5 95% Confidence Interval		Observed Rate	Group 2A, 2B, 2C, 2D: N=12 95% Confidence Interval	
	Lower Bound	Upper Bound		Lower Bound	Upper Bound
0/5	0	0.522	0/12	0	0.265
1/5	0.005	0.716	1/12	0.002	0.385
2/5	0.053	0.853	2/12	0.021	0.484
3/5	0.147	0.947	3/12	0.055	0.572
4/5	0.284	0.995	4/12	0.099	0.651
5/5	0.478	1	5/12	0.152	0.723
			6/12	0.211	0.789
			7/12	0.277	0.848
			8/12	0.349	0.901
			9/12	0.428	0.945
			10/12	0.516	0.979
			11/12	0.615	0.998
			12/12	0.735	1

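### Section 6.3.1: the no-SAE limit of 0.009 for each 12-subject group gives 89.7%, not more than 90%, because the exact limit 0.00874 was rounded up

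*Combined protocol and SAP*

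**What the plan says.** Section 6.3.1 describes the safety sample size through two benchmark rates. The one at issue is "the maximum true rate such that the probability of not observing any event is at least 90" per cent. The section then gives this benchmark for three sample sizes:

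- Group 1, n=5: "over 90% chance to observe no SAE if the true rate is less than 0.021".
- Groups 2A to 2D, n=12 each: "over a 90% chance to observe no SAE if the true rate is no more than 0.009".
- Groups 2A to 2D together, N=48: "greater than a 90% chance to observe no SAE if the true rate is no more than 0.002".

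All three claim a probability above 90%, not merely near it. The n=12 sentence also includes its endpoint, whereas the n=5 sentence excludes it. Table 6-1 gives the chance of no event on a grid of rates but has no row at 0.009 or 0.021.

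**The concern.** The chance of seeing no event falls as the true rate rises. A maximum rate that guarantees at least a given chance must therefore be rounded down. Rounding it to the nearest digit can carry it past the true limit, and the stated inequality then fails at the printed value.

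Safety is the primary endpoint (section 6.2.1), and these sentences are the plan's own account of what its group sizes can show about SAEs. Because Table 6-1 has no row at the quoted rates, a reader cannot check the sentence against the table and has to take it as printed. At stake is the accuracy of a stated operating characteristic, not the design.

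**Working it through.** **Inputs, all from section 6.3.1.** Sample sizes 5, 12 and 48; printed no-SAE limits 0.021, 0.009 and 0.002; required chance of no SAE 0.90.

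**Formulas.** For n subjects and true rate p, exact binomial:

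- chance of no SAE: P(0) = (1 − p)^n
- largest p with P(0) at least 0.90: p = 1 − 0.9^(1/n)

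**Step 1: confirm that this is the plan's method.** For n=12 at p = 0.01, 0.99^12 = 0.886. For n=5 at p = 0.02, 0.98^5 = 0.904. For N=48 at p = 0.01, 0.99^48 = 0.617. All three match Table 6-1, and the rest of that table also reproduces to within rounding.

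**Step 2: reproduce the printed limits, then test them.**

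| n | Exact limit 1 − 0.9^(1/n) | Printed | Direction of rounding | P(0) at printed limit |
|---|---|---|---|---|
| 12 | 0.00874 | 0.009 | up | 0.991^12 = 0.8972 |
| 5 | 0.02085 | 0.021 | up | 0.979^5 = 0.8993 |
| 48 | 0.00219 | 0.002 | down | 0.998^48 = 0.9084 |

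Each printed limit is the exact limit to the nearest third decimal, so the plan's figures are reproduced. The n=12 statement is false at 0.009: the chance of no SAE is 89.7%, and the chance of at least one is 1 − 0.8972 = 10.3%. The n=5 statement excludes 0.021 itself, but rates from about 0.02085 up to 0.021 satisfy it and give 90.0% falling to 89.93%. The N=48 statement holds.

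**Step 3: width of the failing range.** For n=12, 0.009 − 0.00874 = 0.00026. For n=5, 0.021 − 0.02085 = 0.00015. At every rate below the exact limits the chance exceeds 90%.

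**Step 4: does a Poisson approximation rescue the figures?** For n=12, exp(−12 × 0.009) = exp(−0.108) = 0.8976, still below 0.90. For n=5, exp(−5 × 0.021) = exp(−0.105) = 0.9003, so the n=5 figure would pass. The n=12 figure fails under either calculation.

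**Step 5: the companion limits.** The smallest rate with a 90% chance of at least one SAE is 1 − 0.1^(1/n), which is 0.3690, 0.1746 and 0.0468 for n = 5, 12 and 48. The plan prints 0.369, 0.175 and 0.047, giving 0.89997, 0.9006 and 0.9008. The last two were rounded up, which is the safe direction for a minimum rate. The n=5 sentence claims only a "90% chance to observe at least 1 SAE if the true rate is at least 0.369", without saying that it exceeds 90%, so 0.89997 is fair. No change is needed here.

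**The case against.** The best defence is that this is ordinary display rounding. All six limits follow one rule, the nearest third decimal; the formula and inputs are right; and 89.7% is 90% to the nearest whole per cent. That is correct about the cause, and it would fully defend a claim of about 90%. It does not defend a claim of more than 90% at a rate the sentence itself includes.

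For n=5 the defence is nearly complete. The endpoint is excluded, the next lower three-decimal rate is 0.020 with 90.4% (Table 6-1 prints 0.904), and the shortfall is under 0.1 point. That case is no more than an aside.

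It is also fair to say that nothing depends on the figures. Dose escalation and continuation (section 4.3) rest on safety review, and the pause criteria (section 4.5.1) on event counts and on relatedness; neither uses 0.009 or 0.021. Table 6-1 already shows 0.886 at 0.01 for n=12, so a careful reader can see that the limit lies below 0.01. Group sizes are targets, with enrolment up to 70 allowed (section 6.3). One extra subject in a 12-subject group would move the limit from 0.0087 to 1 − 0.9^(1/13) = 0.0081, more than the rounding error.

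A reader might infer that Group 1 and the four 12-subject groups lack the stated property altogether, or that the N=48 limit was handled more carefully than the others. The documents support neither. The property holds up to the exact limits, and N=48 came out right only because 0.00219 happens to round down.

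**Conclusion.** The n=12 sentence is wrong as written, by 0.3 percentage points at its endpoint: 89.7% where more than 90% is claimed. It fails only for rates from 0.00874 to 0.009. The n=5 sentence fails by less than 0.1 point in a still narrower band, and the N=48 sentence is correct. This rests on independent subjects with a common SAE rate and exactly 12 (or 5) subjects per group, which are the assumptions behind the plan's own Table 6-1. The severity is the lowest: a stated figure needs correcting, and no conclusion about the adequacy of the design follows from it.

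**What to change.** In section 6.3.1, state the n=12 limit as 0.0087 (90.05%) or 0.008 (90.8%). Alternatively, keep 0.009 and describe the chance as about 90% (89.7%).

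For consistency, the n=5 limit can become 0.0208 (90.02%) or 0.020 (90.4%). The N=48 limit can stay at 0.002. If all three limits are moved to four decimals, the N=48 value should be 0.0021 (90.4%), because 0.0022 gives 89.97%.

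The cost is one number, or two with the n=5 limit. The stated figures become very slightly less favourable. Tables 6-1 and 6-2, enrolment, decision rules and analyses are untouched.

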6.3.2 Power Calculations for Immunogenicity

Table 6-1 gives the probabilities of observing 0 or more than 1 response over a range of underlying response rates and different sample sizes.

Table 6-2 is applicable to the immunogenic response rates and gives the exact 95% confidence interval of the true response rate over possible number of responses out of the 5 and 12 subjects.

6.3.3 Power for Comparison

As exploratory analyses, we will conduct pairwise comparisons between Groups 2A, 2B, 2C, and 2D of the study for possible differences in immunogenicity; a simple comparison on the positive response rate will be used. **Table 6-3** gives the power of Fisher's exact test to compare the schedules over a range of possible response rates. It indicates that a comparison between the groups is not powered by the study design with 12 samples per group.

Table 6-3: Power to Detect Difference in Response Rates between Any Group by Fisher's Exact Test, Where Both Groups are of Size n=12

	Group Y (N=12)						
		0.1	0.2	0.3	0.4	0.5	0.6
Group Z (N=12)	0.1		2	9	23	42	64
	0.2	2		3	9	21	39
	0.3	9	3		4	9	21
	0.4	23	9	4		4	10
	0.5	42	21	9	4		4
	0.6	64	39	21	10	4	

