1.5 RATIONALE FOR STUDY POPULATION

To assess safety, tolerability, and immunogenicity of the H1ssF_3928 vaccine, subjects 18-70 years of age will be enrolled. In the higher dose group, subjects will be stratified by age into four groups (Groups 2A-2D) to evaluate how the immune responses to the H1ssF_3928 vaccine vary based on age and the likelihood of exposure to different influenza strains.

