6.4.4 Immunogenicity Analysis

The statistical analysis for immunogenicity will employ the intent-to-treat principle whereby all data from enrolled subjects will be analyzed according to the group assignment. However, if during immune assessment on stored samples, a subject is found to have a positive antibody response at baseline, the vaccine immune responses assessment for these subjects will not be included in the final immunogenicity analysis. If needed, a per-protocol analysis will be performed as secondary analysis where subjects will be analyzed according to their actual vaccination scheme if it is different from the assigned or up to the last visit in the study if there are early dropouts. The study is not designed to power the comparison in immune responses between vaccine dosages.

If assay data are qualitative (i.e., positive or negative) then analyses will be performed by tabulating the frequency of positive response for each assay at each time point that an assessment is performed. Binomial response rates will be presented with their corresponding exact 95% confidence interval estimates.

Some immunologic assays have underlying continuous or count-type readout that is often dichotomized into responder/non-responder categories. For these assays, graphical and tabular summaries of the underlying distributions will be made. These summaries may be performed on transformed data (e.g., log transformation) for ease of interpretation.

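### The age comparison rests only on pairwise tests of dichotomised response rates; a baseline-adjusted log-titre model with age group as a factor would use the same samples better.

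*Combined protocol and SAP*

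**What the plan says.** - **Purpose of the strata.** Section 1.5 stratifies the higher-dose group by age to "evaluate how the immune responses to the H1ssF_3928 vaccine vary based on age and the likelihood of exposure to different influenza strains". Under Section 6.3, "Groups 2A, 2B, 2C, and 2D will target 12 healthy adult participants each", 48 in all.
- **Planned comparison.** Section 6.3.3, as exploratory work: "we will conduct pairwise comparisons between Groups 2A, 2B, 2C, and 2D of the study for possible differences in immunogenicity", and "a simple comparison on the positive response rate will be used". Table 6-3 gives the power of Fisher's exact test for 12 against 12 and leads the section to say that "a comparison between the groups is not powered by the study design with 12 samples per group". The section introduces the table as a comparison of schedules, although 2A–2D share one schedule and differ by age.
- **Continuous readouts.** Section 6.4.4 notes: "Some immunologic assays have underlying continuous or count-type readout that is often dichotomized into responder/non-responder categories". For these it plans graphs and tables, on a transformed scale if useful. It plans no regression, overall test across the four groups, trend test or baseline covariate.
- **Who is analysed.** Section 6.4.4 also leaves subjects with a positive baseline antibody response out of the final immunogenicity analysis.
- **Multiplicity.** Section 6.4 waives adjustment for safety and secondary endpoints and does not mention these exploratory comparisons.

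**The concern.** The age strata have one inferential use, and the plan assigns it to a method it has already called inadequate. Part of that weakness comes from the chosen test and not from the 48 subjects. Each comparison uses 24 of them. The titre is reduced to responder or non-responder before any test. The Day 0 titre, which Section 6.2.2 already makes part of the immunogenicity endpoint, is not used to reduce variance.

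A large age effect could therefore go unseen. In the other direction, six unadjusted comparisons give more than one chance of a spurious difference. Either way, the reader gets six p-values and no estimate of how much the titre differs between ages.

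**Working it through.** **1. The plan's own table.** Enumerating both Binomial(12, p) outcomes and rejecting when the two-sided Fisher p ≤ 0.05 reproduces all 15 distinct cells of Table 6-3 to within 0.5 points. Alpha and sidedness are not stated there; 0.05 two-sided fits and 0.05 one-sided does not.

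| Rates | Table 6-3 | Recomputed |
|---|---|---|
| 0.1 v 0.6 | 64 | 63.9 |
| 0.1 v 0.5 | 42 | 42.5 |
| 0.2 v 0.6 | 39 | 39.2 |

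From a rate of 0.1, 80% power needs about 0.69 in the other group. Four groups give 4 × 3 / 2 = 6 pairs. With Bonferroni for six, 0.1 v 0.6 falls from 64% to 29%.

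**2. Inputs for the alternative.** The documents give no log-titre SD, baseline correlation r, responder cut or age effect. Assumed here: SD 1; r = 0.5 (0 and 0.7 as a range); responder cut midway between the group means; D = largest difference between age groups in SD units; 12 per group.

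**3. Age-group factor test.** Adjusting for baseline leaves residual variance 1 − r² = 0.75. The noncentrality is λ = 12 × Σ(μᵢ − μ̄)² / 0.75, with 3 and 48 − 5 = 43 df. For D = 1:
- even decline (0, 1/3, 2/3, 1): Σ = 0.556, λ = 8.9, power 66%
- 2B and 2C low: Σ = 1, λ = 16, power 91%
- only 2B low: Σ = 0.75, λ = 12, power 80%

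**4. Simulation of 4 × 12 subjects, D = 1, r = 0.5.**

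| Age pattern | Factor test, 3 df | Any of six Fisher tests | Linear trend |
|---|---|---|---|
| No effect | 5% | about 11% | 5% |
| Even decline | 63% | 46% | 77–81% |
| Only 2D low | 79–82% | 58–62% | 62–75% |
| 2B and 2C low | 90% | 69% | 4–5% |
| Only 2B low | 80% | 60% | 4–5% |

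The ranges for the trend in the second and third rows run from age in years (lower) to equal group scores (higher). The 4–5% entries are for age in years. Under the even decline, Bonferroni reduces the six Fisher tests to about 13%.

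**5. Sensitivity to r (even decline, D = 1).**
- r = 0: factor 51%, any of six 47%, trend 69%.
- r = 0.7: factor 83%, any of six 47%, trend 94%.

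With no baseline correlation, the factor test's advantage is mainly its correct error rate.

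**6. Smaller effect.** At D = 0.5, r = 0.5, even decline: λ = 8.9 / 4 = 2.2, factor test about 20%. Any of six is also about 20%, and the trend 28–31%.

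**7. Fewer subjects.** For the trend with equal scores, the noncentrality is (D/3) × √(5m) / √(1 − r²), with m per group. At D = 1, r = 0.5:
- m = 12: 0.333 × 7.75 / 0.866 = 2.98, power 83%
- m = 6 (24 subjects left after baseline exclusions): 0.333 × 5.48 / 0.866 = 2.11, power 52%

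The number of baseline positives is not given. Inclusion criterion 3 requires a licensed influenza vaccine since 2014, so some are plausible.

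**The case against.** The plan is open about the limit. It labels the comparison exploratory, says it is not powered, and names no age comparison among the objectives in Section 3. Nothing is miscalculated. The titre is not thrown away either, since Section 6.4.4 summarises its distribution and gives exact intervals for response rates. All this stands, and it makes the point one of missed efficiency. It does not remove the point: the admission of low power concerns Fisher's test on 12 against 12, and the same subjects support a better analysis.

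A reader might go further and infer that a single linear age trend in all 48 subjects is far more powerful at no cost. The documents do not support that, for four reasons:
- Section 1.5 ties age to likely exposure to different strains, which is a birth-cohort rationale with no stated direction. If the middle groups differ, a linear trend has almost no power, and the planned pairwise tests beat it easily.
- The fair comparator is all six Fisher tests, not 2A against 2D alone, which has about 33–36% under the even decline.
- Age in years gives less power than equal group scores, because 18–40 spans 23 years and the other strata 9–11.
- All 48 are not available while Section 6.4.4 removes baseline positives. That rule shrinks the Fisher groups too, so it does not favour the current plan.

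**Conclusion.** The concern holds as an efficiency point about an exploratory analysis. At a 1 SD effect with r = 0.5, the baseline-adjusted age-group test beats the planned comparisons in every pattern examined, by about 17 to 21 points, with less than half the false-positive rate. It also yields adjusted titre ratios with intervals, which for groups of 12 are more useful than p-values. The gain depends on the assumed SD, r, cut and effect size. It is small if r is near 0 and absent for a steady 0.5 SD effect, where no method is adequate. A trend is worth having as a second result only. Table 6-3 is correct, and no safety or secondary conclusion depends on this point.

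**What to change.** In Sections 6.3.3 and 6.4.4, prespecify one exploratory model for each time point (Week 2 and Week 18):
- Outcome log10 titre; covariates log10 Day 0 titre and age group as a four-level factor; Group 2 subjects only.
- Main result: the 3-df age-group test and adjusted group GMT ratios with 95% CIs.
- Secondary: a linear age-trend contrast, with its scoring stated.
- Pairwise response rates with exact CIs, descriptive only, with positive response defined.
- A statement that baseline-positive subjects stay in this model. Section 6.4.4 would otherwise remove them and truncate the covariate.
- A rule for titres below the detection limit.

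In 6.3.3, also replace the reference to schedules with age groups.

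The cost is wording in two sections, including an exception to the baseline-positive rule, plus modest assumptions: roughly normal log titres and the handling of values below the limit. Day 0 samples are already collected, so no subjects or samples are added.
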